8.3.3. Additional Therapy

Additional therapy with AU-011 at the maximum tolerated and feasible dose of 3 repeat doses of 80 µg each followed by two laser applications (treatment regimen) can be provided to:

- ensure that all subjects are able to receive the maximum tolerated and feasible dose, particularly for subjects that were treated with lower doses previously
- allow additional treatment regimens in subjects that have stable disease (treatment extension)
- allow retreatment in subjects that meet the protocol definition of disease progression

If the fovea is near the tumor edge, an adjustment to the laser procedure should be performed on each treatment day as outlined in section 8.2.2 and the Injection and Laser Procedure Manual. Subjects may be considered for additional therapy with AU-011 (defined above) after Visit 11 (Week 12) and only after inflammation from the previous treatment has resolved or when the inflammation is minimal and decreasing based on investigator judgement. Additional therapy with AU-011 must be approved by the Sponsor on a case-by-case basis prior to the initiation of therapy. Alternatively, also after Visit 11 (Week 12 Visit), standard of care therapy, including plaque brachytherapy, proton beam radiotherapy or enucleation may be used if the subject meets the protocol definition of disease progression or the Investigator judges that the disease is progressing per their clinical judgement for increases in tumor thickness or LBD that are less than the protocol definition of disease progression. Before additional therapy is performed, the following protocol assessments must be collected in the study eye unless otherwise noted: ETDRS BCVA (both eyes), slit lamp biomicroscopy, IOP measurement, fundoscopy, Fundus photos, EDI-OCT, B-scan ultrasound, A-scan ultrasound, OCTA (Cohorts 6 to 9 only) and a visual field examination. If these assessments have not been performed at the most recent study visit, an unscheduled visit is required to be performed to obtain these assessments.

The criteria for implementing additional therapy due to disease progression is as follows:

• An increase on B-scan ultrasound of >0.5 mm in melanoma thickness from baseline, not due to intralesional hemorrhage/inflammation

OR

• An increase on digital fundus photos of >1.0 mm in melanoma diameter from baseline, not due to intralesional hemorrhage/inflammation or pigmentary changes

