#### 4.1.2 Visit Windows

The schedule of study assessments can be found in Appendix 11.1 of this SAP.

Missing scheduled visit will be substituted by an unscheduled or early withdrawal visit occurring within each follow-up visit window. If there are multiple unscheduled or early withdrawal visits occurring within the window, the closest one within the visit window will be used. If no unscheduled or early withdrawal visit occurred within the window, the visit will be considered as missing. The details are tabulated in Appendix 11.2.

An exception to this visit-window algorithm is the analysis of the "Last Visit". For all "Last Visit" time-point analyses, a subject's last non-missing endpoint assessment will be used for the analysis, regardless of if the visit falls within a particular visit window or not.

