#### 1. Based on maximum thickness and LBD and subject receiving Standard of Care

Tumor response (PR, SD, or DP) will be based on the algorithm as defined in Section 8.1.1, with the modification that Investigator determination mentioned in DP definition will not be considered and if a subject receives standard of care they will be considered as having met the disease progression (DP) criteria from the date standard of care was administered.

Note that for the Month 12 LOCF and Last Visit timepoints:

- If a patient receives standard of care prior to their Month 12 Visit, the subject will be considered as having met DP, even if the LBD and/or tumor thickness assessments are being LOCF'd from a time-point previous to the SOC being administered.
- Similarly, if a patient receives standard of care prior to their Last Visit, the subject will be considered as having met DP, even if the LBD and/or tumor thickness assessments are being LOCF'd from a time-point previous to the SOC being administered.

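### At Last Visit, standard of care given after a final below-threshold scan with no later visit is scored as tumor control, and two SAP sections disagree on what Last Visit means

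*SAP*

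**What the plan says.** SAP 8.1, Method 1, sets the general rule for subjects who receive SOC: "they will be considered as having met the disease progression (DP) criteria from the date standard of care was administered". For the Last Visit timepoint it adds that "if a patient receives standard of care prior to their Last Visit, the subject will be considered as having met DP", and that this holds "even if the LBD and/or tumor thickness assessments are being LOCF'd from a time-point previous to the SOC being administered". A parallel sentence covers Month 12 with last observation carried forward (LOCF), keyed to SOC before the Month 12 Visit. Methods 2 and 3 start from Method 1, and Method 3 is the primary one for the study report.

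SAP 4.1.2 says that at Last Visit "a subject's last non-missing endpoint assessment will be used for the analysis, regardless of if the visit falls within a particular visit window or not".

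Protocol 8.3.3 sets the order of events around SOC: "Before additional therapy is performed, the following protocol assessments must be collected in the study eye unless otherwise noted". The required list includes fundus photos and B-scan, with an unscheduled visit if they were not done at the most recent visit. The same section permits SOC when protocol-defined progression is met, and also when the Investigator judges the disease to be progressing "per their clinical judgement for increases in tumor thickness or LBD that are less than the protocol definition of disease progression".

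**The concern.** The SOC rule is the only route by which progression judged clinically, below the size limits, can enter the response classification. If it does not fire, the subject is classified on measured size alone and can fall under stable disease (SD), which SAP 8.1.7 counts as tumor control.

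At Last Visit the rule fires only when SOC came first. The protocol puts a scan immediately before SOC, so that scan can be the last one on record. Of two subjects with the same scan and the same radiotherapy, the one who returns afterwards is DP and the one who does not is controlled. The error can only raise the control rate, and it reaches primary Method 3.

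**Working it through.** The plan states no rate or sample-size figure for this point, so there is none to reproduce. The check applies the rules literally to four constructed records.

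**Inputs**
- DP on size: thickness increase > 0.5 mm or largest basal diameter (LBD) increase > 1.0 mm (SAP 8.1.1).
- SOC rule at Last Visit: DP if the SOC date precedes the Last Visit (SAP 8.1, Method 1).
- Reading 1: Last Visit is the last non-missing endpoint assessment (SAP 4.1.2).
- Reading 2: Last Visit is the last visit attended, with sizes possibly carried forward from before SOC (SAP 8.1, Method 1 note).
- Comparison: any recorded SOC counts as DP.

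All four records have SOC on Day 250 and LBD +0.6 mm. Results are for Method 1.

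| Record | Reading 1 | Reading 2 | Any recorded SOC = DP |
|---|---|---|---|
| A. SOC, then scan on Day 300; thickness +0.4 mm | DP | DP | DP |
| B. Scan Day 240, SOC, visit without scan Day 300; +0.4 mm | control | DP | DP |
| C. Scan and last visit Day 240, SOC, no later visit; +0.4 mm | control | control | DP |
| D. As C, but thickness +0.6 mm | DP | DP | DP |

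**Record C** is the gap. Day 250 is not before Day 240, so the Last Visit rule does not fire under either reading. The general rule runs forward from the SOC date, so it leaves Day 240 as SD.

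**Methods 2 and 3 do not rescue record C.** The case report form question in SAP 8.1.2 asks whether protocol-defined progression was met, so No is the correct answer for growth below the limits. Investigator input in SAP 8.1.2 and 8.1.3 only moves DP to SD, and nothing moves SD to DP. Record D would also become SD under Method 2 if the Investigator answered No. The same holds under Method 3, because record D is DP on thickness and SAP 8.1.2 still applies.

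**Record B** is the conflict between the two SAP sections. A programmer following 4.1.2 gets control; one following the Method 1 note gets DP.

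**Size per affected subject**, using planned numbers (up to 15 in Cohort 12, SAP 3.2; approximately 60 in all, SAP 3.3):
- Cohort 12: 1/15 = 6.7 points
- Overall: 1/60 = 1.7 points

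The number affected is not given. If it were 1 to 3 (an assumption), the shift would be 1.7 to 5.0 points of 60, or 6.7 to 20.0 points if all fell in a Cohort 12 of 15.

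**The case against.** A reader might infer that SOC counts only if it preceded the last scan, and that anyone leaving for radiotherapy is counted as controlled. The documents do not support that.

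- **The carry-forward clause.** The Method 1 note expressly scores DP when the sizes predate SOC, provided a later visit exists. SAP 8.1.1 applies LOCF separately to thickness and LBD, so a Last Visit lacking a measurement is foreseen. Version 5.0 of the SAP added detail for exactly these two timepoints.
- **Size-based progression.** A pre-SOC scan above either limit is DP under Method 1 whatever the SOC date, and under Methods 2 and 3 unless the Investigator's answer reclassifies it.
- **Follow-up after SOC.** Protocol 8.3.3 permits SOC within the study, and Protocol 7.3.1 does not list it as a reason to withdraw. SAP 8.3 plans analyses that exclude post-SOC data, so such data are expected. A later visit with an endpoint assessment gives DP under both readings.
- **Month 12.** A reader might call this note wrong for subjects who left before Week 52. It is ambiguous rather than wrong, because Month 12 Visit can be read as the timepoint instead of an attended visit.
- **Capture after exit.** Protocol 8.3 has further treatment documented during the study, and nothing clearly extends this past exit.
- **Visibility.** The analyses are descriptive, additional therapies are tabulated and listed, and the overall response table has a row for subjects given SOC before progressing.

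All of this stands and makes the affected group narrow: growth below the limits, SOC anyway, recorded, and no visit afterwards. It does not close the gap, because no section assigns that record to DP and the SOC row is not said to include SOC after the Last Visit.

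**Conclusion.** The point holds in its narrow form. A protocol-compliant sequence of below-threshold scan, recorded SOC and no further visit is scored as tumor control at Last Visit in all three methods, against the SAP's evident intent. SAP 4.1.2 and the Method 1 note also give opposite answers when the only later visit has no scan. Both effects can only raise the control rate.

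The size is 6.7 points per subject in Cohort 12 and 1.7 points overall, at planned enrolment. Whether any subject is affected cannot be told from the documents. For Month 12 LOCF the finding is only that the cut-off is unclear for a subject without a Week 52 visit. The point merits correction because the bias runs one way and the remedy is small; it does not show that the reported results are materially wrong.

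**What to change.** 1. Reconcile SAP 4.1.2 with the Method 1 note, so that a post-SOC visit without a scan has one defined result.
2. State that at Last Visit a subject is DP if SOC is recorded in the study database on any date after enrolment, including on or after the last assessment. Enrolment is a safer anchor than Day 1, because SAP 4.6 defines Day 1 by first treatment and an untreated Cohort 10 subject has none.
3. For Month 12 LOCF, state that SOC dated on or before the Week 52 visit is DP or, without a Week 52 visit, SOC dated on or before Day 393, the end of the Visit 14 window in SAP 11.2. Say separately how untreated Cohort 10 subjects are handled, since that day count needs a Day 1.
4. Keep the existing row for SOC before progression and say that it includes these cases.

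The cost is a few SAP sentences and a date comparison using the procedure page named in SAP 8.1.4. The reported control rate may be slightly lower. SOC after study exit is reached only where it was recorded, and the report should say so.

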#### 2. Based on maximum thickness and LBD, subject receiving Standard of Care, and Investigators determination of progression

Confidential

Tumor response (PR, SD, or DP) will be based on the algorithm defined method 1 above with the addition of the Investigator determination of progression criteria provided in Section 8.1.2.

3. Based on maximum thickness and LBD, subject receiving Standard of Care, Investigators determination of progression, and adverse events of pigmentary changes

Tumor response (PR, SD, or DP) will be based on the algorithm defined method 1 with the additional criteria of both Investigator determination (Section 8.1.2) and AE of pigmentary changes provided in (Section 8.1.3).

As this method accounts for the Investigator determination of progression per protocol sections 10.3.4 and 10.3.7, it will be considered the primary method for describing the results in the clinical study report.

For each of these 3 methods of determining tumor response, the tumor response results will be presented at each visit, as well as an overall summary table. The overall summary table will present the results at Month 12 using last observation carried forward (LOCF) as well as the subject's last visit, including follow-up. For the overall summary table, the table will provide which of the LBD and maximum thickness criteria were met for the response (or both) as well as a category for "Treated with standard of care prior to Progression" (i.e., this category will be for subjects who were treated with standard of care prior to reaching the progression criteria).

An additional summary of the Summary of Tumor Response Tables (3 tables for Methods 1-3) including just site 009 (i.e., the site excluded from the Efficacy Evaluable Population) will be performed.

#### 8.1.1 Maximum Thickness and LBD Tumor Response Criteria

All tumors will be assessed for thickness by B-scan ultrasound and for largest basal diameter (LBD) by Fundus Photos.

Criteria to classify tumor response will be:

- **Partial Response (PR):**
  - Any reduction > 0.5 mm in the maximum thickness of the CM from baseline (B-scan) and no progression (ie, and increase <1.0 mm) based on LBD (Fundus Photos), **OR**
  - Any reduction > 0.5 mm in the LBD of the CM from baseline (Fundus Photos) and no progression (ie, and increase <0.5 mm) based on tumor thickness (B-scan)
- **Stable Disease (SD):**
  - Maximum thickness of the CM is within -0.5 mm to +0.5 mm (inclusive) change from baseline (B-scan), **AND**
  - Maximum LBD of the CM is within -0.5 mm to +1.0 mm (inclusive) change in diameter from baseline (Fundus Photos)
- **Disease Progression:**
  - Any increase > 0.5 mm in the maximum thickness of the CM from baseline not judged by the Investigator to be due to inflammation/swelling or hemorrhage (B-scan), **OR**
  - Any increase > 1.0 mm in the LBD of the CM from baseline not judged by the Investigator to be due to inflammation/swelling, hemorrhage or pigmentary changes (Fundus Photos)

Confidential

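### SAP 8.1.1: the strict limits printed in the PR definition leave two exact-tie cases, each with shrinkage of more than 0.5 mm in the other dimension, outside PR, SD and DP

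*SAP*

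**What the plan says.** SAP 8.1.1 combines B-scan thickness and fundus-photo LBD into one response class.

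- **PR, first bullet.** "Any reduction > 0.5 mm in the maximum thickness of the CM from baseline (B-scan") together with "no progression (ie, and increase <1.0 mm) based on LBD".
- **PR, second bullet.** "Any reduction > 0.5 mm in the LBD of the CM from baseline (Fundus Photos") together with "no progression (ie, and increase <0.5 mm) based on tumor thickness".
- **SD.** Both dimensions must lie in closed ranges joined by AND: thickness from -0.5 to +0.5 mm, and for the diameter "Maximum LBD of the CM is within -0.5 mm to +1.0 mm (inclusive").
- **DP.** Either dimension is enough: a thickness increase above 0.5 mm, or "Any increase > 1.0 mm in the LBD of the CM from baseline", each subject to the investigator's attribution.

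SAP 4.9 says that these criteria are used in place of the protocol's. SAP 8.1 builds Methods 1, 2 and 3 on 8.1.1, and Method 3 is the primary method for the study report. SAP section 8 takes the average over readers as the analysed value of a continuous measurement.

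**The concern.** The strict limits in the two PR bullets are offered as the meaning of *no progression*. They do not match what the section calls progression. An LBD increase of exactly 1.0 mm, or a thickness increase of exactly 0.5 mm, is not progression under DP and lies inside the SD range, yet it fails the PR condition. If the other dimension has shrunk by more than 0.5 mm, SD is closed as well, and the subject-visit has no class.

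No other rule catches the case. The missing-data rules in 8.1.1 apply only when a measurement is absent. Sections 8.1.2 and 8.1.3 reclassify only subjects who already met DP.

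What is at stake is the PR count and, if the rules are coded literally, the tumor control count (PR plus SD) in 8.1.7. A subject coded as missing would normally leave the percentage denominator under SAP 4.8. Cohort 12 has at most 15 subjects, so one subject is 1/15 = 6.7 percentage points of a proportion in that cohort.

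**Working it through.** The plan gives no figure to reproduce. The check has two parts: the logic of the rules, then the likely frequency of the gap.

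**1. Logic.** Let t be the thickness change and d the LBD change from baseline, in mm. Investigator attribution is left out, as Method 1 directs.

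- PR: (t < -0.5 and d < 1.0) or (d < -0.5 and t < 0.5)
- SD: -0.5 ≤ t ≤ 0.5 and -0.5 ≤ d ≤ 1.0
- DP: t > 0.5 or d > 1.0

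| t | d | Class as printed | Class with ≤ in the PR bullets |
|---|---|---|---|
| -0.8 | +0.99 | PR | PR |
| -0.8 | +1.00 | none | PR |
| -0.8 | +1.01 | DP | DP |
| +0.49 | -0.8 | PR | PR |
| +0.50 | -0.8 | none | PR |
| +0.51 | -0.8 | DP | DP |
| -0.5 | +1.0 | SD | SD |
| +0.5 | -0.5 | SD | SD |

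Every pair (t, d) from -3.00 to +3.00 mm was enumerated in integer arithmetic, so that ties are exact.

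| Step | Pairs | No class, as printed | More than one class, as printed | No class or more than one, with ≤ |
|---|---|---|---|---|
| 0.01 mm | 601² = 361,201 | 500 | 0 | 0 |
| 0.05 mm | 121² = 14,641 | 100 | 0 | 0 |
| 0.10 mm | 61² = 3,721 | 50 | 0 | 0 |

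All unclassified pairs fall in two sets of equal size: d = +1.0 with t < -0.5, and t = +0.5 with d < -0.5. These are counts of grid points, not patient probabilities.

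**2. Frequency.** The documents state no measurement precision, no SD of change and no correlation between the two changes. Everything here is assumed: normal changes with mean zero, SD 0.3-0.4 mm for thickness and 0.5-0.8 mm for LBD, and values recorded on a grid of width g. If the changes are independent,

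P(gap) = P(t in the cell at +0.5) × P(d < -0.5) + P(d in the cell at +1.0) × P(t < -0.5),

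where a cell is the limit ± g/2.

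- g = 0.05, SDs 0.3 and 0.5: 1.66% × 15.87% + 0.54% × 4.78% = 0.26% + 0.03% = 0.29%
- g = 0.1, SDs 0.4 and 0.8: 4.57% × 26.60% + 2.28% × 10.57% = 1.22% + 0.24% = 1.46%

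The gap needs the two dimensions to move in opposite directions, so a positive correlation shrinks it. Averaging over readers makes the grid finer, which also shrinks it.

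| Scenario | SDs 0.3 and 0.5 | SDs 0.4 and 0.8 |
|---|---|---|
| Independent (g = 0.05 left, 0.1 right) | 0.29% | 1.46% |
| Correlation 0.3, same grids | 0.10% | 0.78% |
| Correlation 0.5, same grids | 0.03% | 0.38% |
| Independent, g = 0.01 | 0.06% | 0.15% |

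**The case against.** The best defence is that the operative words are *no progression* and the parenthesis only explains them. DP, a few lines below, fixes progression at strictly above 1.0 mm and 0.5 mm, and the SD ranges treat both limits as non-progression. On that reading both tie cases are PR and nothing is left open. As to intent, this stands. It does not rescue the text, because a programmer who codes the printed inequalities gets no class.

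Three stronger readings are tempting, and the documents do not support them.

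- *Someone must choose a class after seeing the data.* The section's own wording points to PR, so a data-driven choice is not forced.
- *Any shrinkage combined with a change at the limit is unclassified.* With shrinkage of 0.5 mm or less the case is SD, as the last two rows of the first table show.
- *The tumor control rate is necessarily damaged.* SAP 8.1.7 counts control on both dimensions against progression on either. Taken one dimension at a time, a tied subject is controlled on both. Since 8.1.7 refers back to the definitions in 8.1, this is arguable either way. If the case is read as PR, the control count is intact.

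It is also fair to say that the stakes are low. No hypothesis is tested, results are descriptive, and SAP section 4 promises listings of individual values, so a tie could be found.

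**Conclusion.** The concern holds as a wording error in a decision rule: the limits printed in the two PR bullets contradict the DP and SD limits beside them. Under the printed rules, with investigator attribution set aside, exactly two sets of tied values have no class. All three response methods inherit the error.

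The practical effect is small. It requires an exact tie together with shrinkage of more than 0.5 mm in the other dimension. The estimates run from about 0.03% to about 1.5% of subject-visits. The upper end requires independent changes and a coarse 0.1 mm grid, and reader averaging makes so coarse a grid less likely. The whole range rests on assumed SDs, zero mean change and normality. This is a correction worth making, not a threat to the trial's conclusions.

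**What to change.** In the two PR bullets of SAP 8.1.1, replace <1.0 mm by ≤1.0 mm and <0.5 mm by ≤0.5 mm. Equivalently, delete the parentheses and define *no progression* as not exceeding the DP limits. Either change gives every pair of changes exactly one class. State as well the rounding applied to averaged reader values before classification, because floating-point error can otherwise decide a tie.

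The edit is small, but it is not free of process. SAP v5.0 was written after the first database lock on 25 Aug. 2021, so this would be a further post-lock revision and should be logged as one. It moves tied cases into PR, so the study report should state how many subject-visits it affects, even if the number is zero.

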7.1. Subject Inclusion Criteria

Subjects must:

- 1. Be at least 18 years of age of either gender or any race.
- 2. Have been informed about the nature and requirements of the study, voluntarily agreed to participate in the study, and documented this by signing the Informed Consent Form (ICF) before participating in any study-related activities.
- 3. Be willing and able to follow all instructions and attend all study visits.
- 4. Per the expert opinion of the Investigator, have clinically diagnosed primary CM with no known metastatic disease.
- 5. Have clinically diagnosed primary CM:
 - A. with tumor thickness of ≥ 1.2 mm and ≤ 3.0 mm on B-scan ultrasound and with a largest basal diameter of ≤ 13.0 mm on fundus photos associated with tumor growth,

OR

- B. with tumor thickness of ≥ 2.0 mm and ≤ 3.0 mm on B-scan ultrasound and with a largest basal diameter of ≤ 13.0 mm on fundus photos associated with the presence of subretinal fluid by OCT AND at least one of the following:
 - a. Overlying orange pigment (lipofuscin) on fundus photos
 - b. Vision loss
 - c. Flashes or floaters

OR

C. Criteria for Cohort 12: with tumor thickness of ≥ 0.5 mm and ≤ 3.0 mm on B-scan ultrasound, a largest basal diameter of ≤ 13.0 mm on fundus photos with an estimated tumor volume ≤ 50 mm³ associated with tumor growth within 2 years of screening (defined as ≥ 0.4 mm increase based on intersite measurements or ≥ 0.3 mm based on within site measurements on tumor thickness)

NOTE: Whenever available at the investigative site or referring site, historical images (B-scans and/or color fundus photos) for all subjects should be provided to the Independent Reading Center at the time of entry to the study. The investigative site should make all reasonable efforts to obtain this information from referring sites.

- 6. In the opinion of the treating physician, the subject could be managed by interventional therapy, or by cautious observation.
- 7. Be treatment-naïve for their primary CM.

- 8. Have a tumor for which the entire extent must be able to be imaged on required fundus photography in a single frame and treated by the laser.

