8.3.4. AU-011 Treatment Criteria for Observation Cohort

Once tumor growth is established in the observation cohort as described below, subjects will receive the first of 2 cycles of AU-011 treatment and the visit schedule for treatment and follow-up is described in Section 10 and Appendix 1 of this protocol until Cycle 2 is administered, at which time the visit schedule in Appendix 4 will be followed.

The criteria for confirming tumor growth in subjects in the observation cohort are as follows:

• A growth rate of 0.5 mm per year (with a minimum detectable increase of 0.15 mm over a minimum period of 3 months) in melanoma thickness from baseline or an absolute increase of ≥ 0.5 mm during the study period

OR

• A growth rate of 1.0 mm per year (with a minimum detectable increase of 0.6 mm over a minimum period of 3 months) in melanoma LBD from baseline or an absolute increase of ≥ 1.5 mm during the study period

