### 4.2 Planned analyses

Two interim analyses are planned: 1) after the first 2 cohorts (SAD cohorts) have completed 12 months of follow-up (Visit 14); and 2) after all subjects complete Week 12 visit (Visit 11).

The final analysis will be performed when all enrolled subjects will have completed the End of Study visit or the Early Termination visit, if early discontinued from study.

Note on SAP V2.0:

- 1) One interim analysis was performed for the '01AUG2018 Deliverable'.
- 2) No further interim analyses are going to be done.
- 3) Due to the early termination of the study, the final analysis will be performed after all subjects complete the Week 52 Visit.

Confidential

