### **Missing LBD or maximum thickness values:**

If both the LBD and maximum thickness values at a visit are missing, the tumor response will be set to missing for that visit.

If 1 of the 2 measurements is missing, the tumor response will be determined by just considering criteria as applied to the non-missing measurement. (note: this rule does not apply to the Month 12 LOCF and Last Visit endpoints where an LOCF algorithm for both tumor thickness and LBD will be applied, as described below).

Additionally, the following LOCF algorithm for tumor thickness and LBD will be applied for tumor response relative the Month 12 LOCF and Last Visit endpoints only (i.e., this LOCF algorithm does not apply to the individual visits, only the Month 12 LOCF and Last Visit timepoints).

- If a subject is missing a tumor thickness and/or their LBD assessments as a scheduled visit, an LOCF approach will be used to impute the missing data from the previous visits (ie, an LOCF approach will be applied to the tumor thickness and separately an LOCF approach will be applied to the LBD). If a patient has no non-missing post-baseline visits, the baseline value will be used. The assessment of tumor response (i.e., as described above) will be applied using the LOCF'd tumor thickness and LBD values.

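### Month 12 and Last Visit tumor control counts subjects with no post-baseline scan as stable, and no sensitivity analysis tests how missing scans are handled

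*SAP*

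**What the plan says.** **Response limits.** SAP 8.1.1 requires two things for stable disease (SD): "Maximum thickness of the CM is within -0.5 mm to +0.5 mm (inclusive) change from baseline (B-scan", and an LBD change from -0.5 to +1.0 mm inclusive. Progression (DP) is an increase above +0.5 mm in thickness or above +1.0 mm in LBD. SAP 8.1.7 counts partial response and SD together as tumor control.

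**Missing scans.** In the by-visit tables, response is missing if both measures are missing, and is judged on the remaining measure if one is missing. The Month 12 LOCF and Last Visit summaries work differently. Thickness and LBD are each carried forward from earlier visits, and "If a patient has no non-missing post-baseline visits, the baseline value will be used".

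**Populations.** SAP 4.3.1 puts every enrolled subject in the ITT population, treated or not, and makes it primary for efficacy. Under SAP 4.4 the documented-growth (DG) subgroup accepts any amount of thickness growth. Cohort 12 entry (Protocol 7.1, criterion 5C) needs growth of at least 0.3 "mm based on within site measurements on tumor thickness", or 0.4 mm between sites, within 2 years of screening.

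**Timing.** SAP 4.2 states that "the final analysis will be performed after all subjects complete the Week 52 Visit", because the study ended early.

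**The concern.** A missing scan carries no information about tumor growth, yet at Month 12 and Last Visit the rule turns it into a favourable result. If the baseline value stands in for both measures, the change is zero on each and the subject is SD, hence controlled. A scan from the first months does nearly the same, because little growth can have accumulated by then. If dropout or missed imaging is at all common, the overall control rate is pushed up by data that were never collected.

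A second weakness makes this matter more. The SD ceiling is wide relative to the slow growth that qualifies a subject for Cohort 12 or the DG subgroup. A slow-growing tumor can be scored SD without any treatment effect. Protocol 4.6 expects treated tumors to show as stable disease, so readers will look to this rate for evidence of efficacy.

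**Working it through.** The documents state no sample-size basis, expected control rate or missing-data rate, so there is no plan figure to reproduce.

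**Inputs from the documents.** SD limits of +0.5 mm thickness and +1.0 mm LBD (SAP 8.1.1). Target days 85, 183, 274, 365 and 728 for Weeks 12, 26, 39, 52 and 104, and a Week 52 window of Day 337-393 (SAP 11.2). Reference growth rate of 0.5 mm/year in thickness (Protocol 8.3.4). Cohort 12 entry minimum of 0.3-0.4 mm over 2 years, that is 0.15-0.20 mm/year.

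**Assumptions, not in the documents.** Linear growth. Normal measurement error with standard deviation of thickness change (s) 0.1-0.3 mm. Missing share m of 10-30%.

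**Formulas.** Change = rate × (day − 1)/365.25. Probability of being scored controlled on thickness = Φ((0.5 − change)/s). The lower SD limit of -0.5 mm is ignored because a larger reduction is partial response, provided the other measure has not progressed.

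**Step 1: carried-forward scans, tumor growing 0.5 mm/year.**

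| Scan used at Month 12 | Thickness change (mm) | Probability controlled, s = 0.3 to 0.1 |
|---|---|---|
| Baseline | 0 | 1 by rule |
| Week 12 | 0.5 × 84/365.25 = 0.115 | 0.90-1.00 |
| Week 26 | 0.5 × 182/365.25 = 0.249 | 0.80-0.99 |
| Week 39 | 0.5 × 273/365.25 = 0.374 | 0.66-0.90 |
| Week 52, observed | 0.5 × 364/365.25 = 0.498 | 0.50-0.51 |

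The same tumor is therefore scored controlled far more often from an early scan than from the scan that should have been taken.

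**Step 2: effect on the group rate.** Rate = (1 − m) × P(Week 52) + m × P(carried scan).

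- m = 10%, Week 26 carried, s = 0.3: 0.9 × 0.502 + 0.1 × 0.798 = 0.532, a rise of 3 points.
- m = 10%, baseline carried, s = 0.3: 0.9 × 0.502 + 0.1 = 0.552, a rise of 5 points.
- m = 30%, Week 26 carried, s = 0.3: 0.7 × 0.502 + 0.3 × 0.798 = 0.591, a rise of 9 points.
- m = 30%, baseline carried, s = 0.3: 0.7 × 0.502 + 0.3 = 0.652, a rise of 15 points.

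These figures use thickness alone.

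**Step 3: slow growth against the SD limit.**

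| Rate (mm/year) | Week 52 change (mm) | Week 104 change (mm) | Years to reach +0.5 mm |
|---|---|---|---|
| 0.15 | 0.149 | 0.299 | 0.5/0.15 = 3.3 |
| 0.20 | 0.199 | 0.398 | 0.5/0.20 = 2.5 |

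The probability of being scored controlled on thickness is 0.84-1.00 at Week 52 and 0.63-0.98 at Week 104.

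**Step 4: what the move to Week 52 changes.** Without error, thickness exceeds +0.5 mm above about 0.5 mm/year at Week 52 and above about 0.5/2 = 0.25 mm/year at Week 104. The earlier analysis therefore loses discrimination only in the band of about 0.25-0.5 mm/year.

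**Step 5: whether another analysis covers it.** SAP 8.3 varies the population (with or without site 009) and the use of data after standard of care. It does not vary how missing scans are handled.

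**The case against.** Several provisions limit the problem. Standard of care before Month 12 or Last Visit is scored DP even when earlier scans are carried forward (SAP 8.1, Method 1). The by-visit tables, including Week 52, use no LOCF. B-scans are scheduled often in the first 12 weeks, and early leavers are asked for exit imaging (Protocol 7.3.3, 10.3.7), so a subject with no post-baseline scan should be rare. SAP 8.1.8 plans a mixed-model comparison of post-treatment with historical thickness growth, including in the DG subgroup. The primary objective is safety and nothing is tested.

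All of this is true and it bounds the size of the problem. It does not remove it. The standard-of-care rule does not reach a subject who leaves with no such treatment recorded. The by-visit tables keep the same cut-offs. The growth-rate comparison goes to a separate sponsor report. Frequent early visits make baseline carry-forward less likely, but make a carried early scan more likely.

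One caveat applies to never-treated subjects. SAP 4.6 ties baseline to the first treatment day, so they become SD under this rule only if a screening scan is taken as baseline.

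A reader might also infer that the move to Week 52 makes a tumor at the protocol's own growth threshold ("A growth rate of 0.5 mm per year (with a minimum detectable increase of 0.15 mm over a minimum period of 3 months") score as controlled. That is a knife-edge. Across the Day 337-393 window its change runs from +0.460 mm (SD) to +0.537 mm (DP), and with symmetric error it is controlled about half the time. A tumor meeting the 3-month minimum increase of 0.15 mm grows at 0.60 mm/year and would be at about +0.60 mm, which is DP.

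**Conclusion.** The concern holds for missing-scan handling. A subject with no post-baseline scan and no recorded standard of care is tumor control by construction at Month 12 and Last Visit, early scans carried forward favour SD, and no planned sensitivity analysis shows how much this matters. For a 0.5 mm/year tumor the rise is roughly 3-15 points at 10-30% missing. That range rests on the assumed missing share, linear growth, normal error with s of 0.1-0.3 mm, and thickness alone.

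It also holds that the SD rate by itself is weak evidence of effect. Growth at the Cohort 12 entry minimum, or slower growth admitted to the DG subgroup, would usually be SD on thickness without treatment. This comes mainly from the cut-off: at the entry minimum the result is the same at Week 104, and the move to Week 52 adds to it only for about 0.25-0.5 mm/year.

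Three stronger inferences are not supported:

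- That control is near automatic for the whole group. This applies only to imputed subjects, and their share is not stated.
- That most untreated tumors would be scored controlled. The documents give no growth-rate distribution, and 0.3 mm is a minimum for entry.
- That a given thickness rate is necessary for DP. DP can also be reached through LBD.

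**What to change.** 1. **SAP 8.1.1.** Delete the baseline carry-forward for both Month 12 LOCF and Last Visit. Report subjects with no post-baseline scan and no standard of care as not assessable, kept in the denominator and not counted as tumor control.

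2. **SAP 8.3.** Add a Month 12 sensitivity analysis that uses only scans in the Week 39 (Day 246-302) or Week 52 (Day 337-393) windows. Count a subject with neither as not controlled, unless already DP. Show the number imputed in the main summary by source visit. Label the analysis as added after the first database lock, which SAP section 2 dates to 25 August 2021.

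3. **Optional, for DG and Ph3 Elig.** Show tumor control among subjects whose own pre-treatment thickness rate projects above +0.5 mm at Week 52. SAP 8.1.8 already needs those rates.

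The cost is SAP wording and a few table rows, with no new data. The control rate may become slightly less favourable, the group in item 3 will be small, and the change comes after a lock and must be disclosed as such.
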